Patients who have been receiving treatment at CTCA and have been receiving outpatient PN and develop PNinduced hepatic injury, or will be starting home PN and have existing hepatic dysfunction.

Patients will receive their initial infusion of PN containing Omegaven at a CTCA location to observe for adverse reactions. Omegaven will be given on Day 1 at a dose of 0.1 g/kg body weight (1 mL/kg). On Day 2 or 3, it will be increased to 0.2 g/kg body weight (2 mL/kg). The infusion rate will not exceed 0.5mL Omegaven/kg body weight/hr (corresponding to 0.05g fish oil/kg/hr).

After tolerance is established, patients will have the option to receive treatment at home through Coram for 4 weeks or until hepatic dysfunction is reversed (established normalization of liver function tests/serum bilirubin < 2).

INCLUSION CRITERIA:

A patient must meet the following criteria to participate in this study:

- I.1 Male or Female; ages 18 to 80
- **I.2** Receiving treatment at CTCA
- **I.3** Receiving PN (either in the infusion center or at home)
- I.4 Have existing hepatic dysfunction defined as Elevation of >3x the normal level of one or more of the following: Alkaline Phosphatase (ALP), Aspartate Aminotransferase (AST), or Alanine Aminotransferase (ALT) and/or Bilirubin > 2 mg/dl in the absence of biliary obstruction.
- **1.5** Able to provide informed written consent (patient or legally acceptable representative)

EXCLUSION CRITERIA:

Patients will be excluded from participating in the study for the following reasons:

- **E.1** Hypertriglyceridemia (fasting triglycerides [TG] > 400)
- E.2 Allergy to fish or egg protein
- **E.3** Currently on therapeutic doses of Coumadin, heparin, or low molecular weight heparin.
- **E.4** Hemodynamically unstable
- **E.5** Bilirubin > 5 mg/dL
- **E.6** Documented progression of liver metastases
- **E.7** Unstable diabetes with known diabetic ketoacidosis within 7 days of screening
- E.8 Recent cardiac infarction taking plavix
- **E.9** Severe hemorrhagic disorders

E.10 Embolism

- E.11 Sepsis
- **E.12** Undefined coma status
- **E.13** Renal insufficiency with calculated creatinine clearance < 30 mL/min.
- **E.14** Pregnancy or lactation

TREATMENT:

Treatment with Omegaven will be given on study Day 1 at a dose of 0.1 g/kg body weight (1 mL/kg). On Day 2 or 3, it will be increased to 0.2 g/kg body weight (2 mL/kg). The infusion rate will not exceed 0.5mL Omegaven/kg body weight/hr (corresponding to 0.05g fish oil/kg/hr).

Omegaven will be co-infused via y-site. Containers will be changed every 12 hours. Omegaven will be given through a 1.2 micron inline filter.

Omegaven will be given daily for:

- Up to 4 weeks, or
- Until normalization of alkaline phosphatase, AST, & ALT

The patient may receive other lipids to meet essential fatty acid (EFA) and/or additional calorie needs.

EFFICACY OUTCOME VARIABLES:

- Maximum conjugated bilirubin
- Time to resolution of bilirubin or death
- Average improvement in bilirubin, alkaline phosphatase, AST, & ALT

SAFETY OUTCOME VARIABLES:

- Summary of laboratory results
- Summary of AEs for each patient

			Table of Contents	
1.	LIST OF ABBREVIATIONS AND DEFINITIONS OF TERMS			6
2.		INTRO	DUCTION	7
	2.1.	Backgrou	nd	7
	2.2.	Risk Cate	gory	8
	2.3.	Rationale)	8
	2.4.	Statemer	nt	8
3.		OBJEC	ΓΙVES	8
4.		INVEST	IGATONAL PLAN	9
	4.1.	Study De	sign	9
	4.2.	Study Pro	ocedures by Visit	10
		4.2.1. S	creening Visit	10
		4.2.2. C	Day 1 Visit	10
		4.2.3. E	Day 2/Day 3 Visit	10
		4.2.4. C	Day 5 Visit	10
		4.2.5. V	Neekly Visits During Home Use of Omegaven (up to 4 weeks of treatment)	11
		4.2.6. F	inal Study Visit/Early Withdrawal Visit	11
	4.3.	Description	on of Study-Specific Procedures	11
		4.3.1. C	Diagnostic Tests	11
5.		SELECT	ION AND WITHDRAWAL OF PATIENTS	12
	5.1.	Patient Ir	clusion Criteria	12
	5.2.	Patient E	xclusion Criteria	12
	5.3.	Patient W	/ithdrawal Criteria	12
6.		CONCO	OMITANT MEDICATIONS/TREATMENT	13
7.		COMPI	LIANCE	13
8.		INVEST	IGATIONAL MATERIALS AND MANAGEMENT	13
	8.1.	Investiga	tional Product	13
		8.1.1. 0	General Investigational Product Information	13
		8.1.2. C	Dosing	14
		8.1.3. C	Dispensation	14
		8.1.4. 5	torage and Handling	14
		8.1.5. A	Accountability	14
		8.1.6. C	Dose Adjustments	14
9.		ASSESS	MENT OF EFFICACY AND SAFETY	14
	9.1.	Outcome	Variables	14
	9.2.	Adverse I	Event (AE) Recording/Reporting	14
	9.3.	Serious A	dverse Event (SAE) Recording/Reporting	16
	9.4.	IND Safet	y Reporting	16
		9.4.1. V	Vritten IND Safety Report	17
		9.4.2. T	elephone or Fax IND Safety Reports	17
	9.5.	IRB Safet	y Reporting	17
10.		DATA I	MANAGEMENT	17
	10.1.	Data Mar	nagement	17
	10.2.	Sample S	ize Determination	17
	10.3.	Dispositio	on and Baseline Assessment	17
	10.4.	Outcome	s Analysis	17
	10.5.	Data Mor	nitoring Committee	18
	10.6.	Study Ter	mination	18

	10.7.	Study Medication Administration	. 18
	10.8.	Concomitant Medications	. 18
11.		STUDY ADMINISTRATION	. 18
	11.1.	Adherence to the Protocol	. 18
	11.2.	Amending the Protocol	. 19

1. LIST OF ABBREVIATIONS AND DEFINITIONS OF TERMS

Abbreviation/Term	Definition
AE	Adverse Event
ALP	Alkaline Phosphatase
ALT	Alanine Aminotransferase
AST	Aspartate Aminotransferase
BUN	Blood Urea Nitrogen
CO ₂	Carbon Dioxide
CRF	Case Report Form
CRO	Contract Research Organization
CRP	C-Reactive Protein
CTCA	Cancer Treatment Centers of America
DCF	Data Clarification Form
DHA	Docasahexaenoic Acid
DMC	Data Monitoring Committee
EFA	Essential Fatty Acid
EPA	Eicosapentaenoic Acid
G	gram
GCP	Good Clinical Practice
GGT	Gamma-Glutamyl Transferase
Hbg	Hemoglobin
Hct	Hematocrit
Hr	hour
ICF	Informed Consent Form
ICU	Intensive Care Unit
INR	International Normalized Ratio
IRB	Institutional Review Board
Кд	kilogram
LDH	Lactic Acid Dehydrogenase
LOS	Length of Stay
MCH	Mean Corpuscular Hemoglobin
МСНС	Mean Corpuscular Hemoglobin Concentration
MCV	Mean Corpuscular Volume
MedDRA	Medical Dictionary for Regulatory Activities
mg/dL	Milligram per deciliter
mL	Milliliter
ml/kg	Milliliters per kilogram
MPV	Mean Platelet Volume
NCR	No Carbon Required
PN	Parenteral Nutrition
PT	Prothrombin Time
PTT	Partial Thromboplastin Time
RBC	Red Blood Count
RDW	Red Cell Distribution Width
SAE	Serious Adverse Event
TG	Triglycerides
TNF	Tumor Necrosis Factor
WBC	White Blood Count
WHODDE	World Health Organization medical dictionary
<	Less than
>	Greater than
=	Equal to

Table 1: List of Abbreviations and Definitions of Terms

2. INTRODUCTION

2.1. Background

Parenteral nutrition (PN), when required for long-term nutrition support, may lead to hepatic dysfunction (ADA pocket guide to PN). PN can be the cause of hyperbilirubinemia and elevated liver function tests. Patients at increased risk of developing hepatic dysfunction from PN are those with primary gastrointestinal disorder, pre-existing liver disease, malnutrition, or sepsis (ref). The cause of this dysfunction may be related to the provision of excess calories, excess individual macronutrients, and deficiencies of choline, L-carnitine, and/or glutamine. This dysfunction can progress to liver failure in patients requiring long-term PN.

There are recommendations to try to prevent PN induced hepatic dysfunction. They include but are not limited to avoiding excess calorie, carbohydrate, and/or lipid infusion; limiting infusion time; some oral or enteral nutrients if possible; and possibly adding choline, L-carnitine, and/or glutamine to the PN. Despite following these recommendations, patients may still develop PN induced hepatic dysfunction. This may result in the need to discontinue PN.

Patients with advanced cancer requiring PN for long-term nutrition support may be at increased risk for developing this condition due to gastrointestinal failure, liver metastases, and malnutrition. If these individuals begin to experience elevation of bilirubin and/or liver function tests, the calories from macronutrients may have to be reduced, resulting in underfeeding in those that may already be malnourished. If after reducing calories from macronutrients and adding L-carnitine to the PN, liver function does not improve, the PN may have to be held or discontinued. This results in severe under nutrition or in some cases no source of nutrition.

Lipid emulsions are added to parenteral nutrition to provide calories and essential fatty acids. Currently, the lipid emulsions used in the United States (U.S.) are long chain triglycerides from soybean or safflower oil, which have a high ratio of n-6 to n-3 polyunsaturated fatty acids (Wanten 2007). There is some evidence to suggest that the n-6 lipid emulsions used in PN may be associated with PN induced steatohepatitis and an increase in pro-inflammatory eicosanoids resulting in immune suppression (Wanten 2007, Kinsella 1990). Omega-3 fatty acid containing lipid emulsions are not available in the U.S., but they are available and are being studied in Europe and Taiwan. Omega-3 fatty acid containing lipid emulsions have been shown to prevent or attenuate PN-induced hepatosteatosis in normal rats and mice (Chen 1996, Alwayn 2005). In addition, these solutions have been shown to ameloriate diet-induced hepatosteatosis in rats (Yeh 1996). Most recently, in a non-randomized study using historical controls, 18 infants with short-bowel syndrome who developed cholestasis, were given a fish-oil based fat emulsion. Reversal of cholestasis was achieved 4.8 times faster (9.4 weeks vs. 44.1 weeks) in those receiving the fish oil emulsion compared to historical controls that received soybean emulsions. Also, the fish-oil based emulsion was safe and was not associated with essential fatty acid deficiency, hypertriglyceridemia, coagulopathy, or infection (Biank 2008).

In addition to the potential role omega-3 lipid emulsions may play in reversing PN induced hepatic injury, they may help decrease the inflammatory response and have a beneficial effect on clinical outcomes. Morlion et al. (1996) found that 5-days of a parenteral fish oil supplement resulted in a change in leukotriene synthesis to a more favorable 5 series and a decreased length of stay in surgical patients. Pluess et al. (2007) demonstrated that a two day infusion of a fish-oil emulsion (Omegaven) in healthy volunteers given an endotoxin increased eicosapentaenoic acid (EPA) and docasahexaenoic acid

(DHA) content in platelet phospholipids and decreased tumor necrosis factor alpha compared to controls.

Other studies have found a decrease in intensive care unit (ICU) days and length of stay with fish-oil emulsions. Heller et al. (2006) in a prospective, open label, multiple-center trial found that administration of a fish-oil emulsion reduced mortality, antibiotic use, and length of stay in different diseases. A total of 661 patients receiving PN for \geq 3 days were included in the study to evaluate dose-dependent effects of fish-oil emulsion. The mean dose given was 0.11 g/kg/day. The most favorable effects on survival, infections, and length of stay were at doses of 0.1 and 0.2 g/kg/day. Antibiotic use was lowered by 26% with doses of 0.15-0.2 g/kg/day. Finally, a dose of 0.23 g/kg/day was associated with a decrease in ICU LOS. No bleeding or other adverse events were reported.

Heller et al. (2004) also found that fish oil supplemented PN improved liver and pancreas function in a prospective, randomized, double-blind clinical trial on 44 patients having major abdominal cancer surgery. Patients were randomized to receive either PN with soybean oil or a combination of soybean and fish oil for 5 days. The fish oil group had reduced AST, ALT, & bilirubin after surgery. The fish oil group also trended towards having a shorter ICU stay. Also, the soybean only group lost 1.1±2.2 kg, while the fish oil group did not lose weight.

In a prospective, double-blind, randomized, controlled study of 42 patients requiring radical resection for colon cancer, Liang et al. (2008) found a favorable effect on the inflammatory and immune response with the use of an omega-3 lipid emulsion postoperatively. All patients received PN for 7 days postoperative. The control group received standard omega-6 lipid emulsion while the study group had some of the omega-6 lipid in their PN replaced with omega-3. On post-op day 8, serum IL-6 levels were significantly lower with omega-3. Also, with omega-3, the ratio of CD4+/CD8+ was significantly increased; TNF- α was decreased; and CD4+ lymphocyte percentage was increased.

2.2. Risk Category

(45 CFR 46.405) Category 2: Research involving greater than minimal risk, but presenting the prospect of direct benefit to the individual patients.

2.3. Rationale

Omegaven may be effective in stabilizing or reversing hepatic injury associated with the use of PN. In addition, omega-3 lipid emulsions may help decrease the inflammatory response and have a beneficial effect on clinical outcomes. This compassionate use protocol provides a mechanism for physicians to better understand the efficacy of Omegaven for the treatment of patients with advanced cancer requiring PN for long-term nutrition support who have developed PN-induced hepatic injury or who have existing hepatic dysfunction.

2.4. Statement

This study will be conducted in compliance with the protocol, the guidelines of Good Clinical Practices (GCP), the current revision of the Declaration of Helsinki, and the applicable regulatory requirements.

3. OBJECTIVES

The primary objective for this study is to examine if an omega-3 based lipid emulsion (Omegaven) can improve or prevent further deterioration of PN induced hepatic dysfunction.

The secondary objective for this study is to examine the effect of an omega-3 based lipid emulsion (Omegaven) on immune function and markers of the inflammatory process.

4. INVESTIGATIONAL PLAN

4.1. Study Design

This compassionate use study will include patients with advanced cancer requiring PN for long-term nutrition support who have developed PN-induced hepatic injury or who have existing hepatic dysfunction. Therapy with Omegaven will be provided at an initial dose of 0.1 g/kg body weight (1ml/kg) and increased to 0.2 g/kg body weight (2ml/kg) on day 2 or 3 of treatment. For patients > 120% ideal body weight, adjusted body weight will be used. The infusion rate will not exceed 0.5mL Omegaven/kg body weight/hr (corresponding to 0.05g fish oil/kg/hr). Omegaven will be co-administered via a y-site infusion, with containers being changed every 12 hours. The patient may receive other lipids to meet Essential Fatty Acid (EFA) and/or additional calorie needs. Patients will receive the initial infusion of PN containing Omegaven at Midwestern Regional Medical Center (MRMC) in the infusion center to observe for adverse reactions. If an adverse reaction is observed, IV steroids & benadryl will be administered & Omegaven will be discontinued. Patients will continue to receive infusions at CTCA for the first 2 to 3 days of dosing. After tolerance is established, patients will receive treatment at home with Coram. All study patients will have a Screening Visit; Day 1, Day 2 and Day 3 visits; and weekly visits for one month (see Table 2).

					Weekly	Final Study Visit/
Visit:	Screening	Day 1	Day 2	Day 3	Visits	Early Withdrawal
Informed Consent Form	Х					
Inclusion/Exclusion Criteria	Х					
Physical Exam	Х					Х
Vital Signs	Х	Х	Х	х	Х	Х
Medical History	Х					
Blood hematology/chemistry	Х	Х	Х	Х	Х	Х
Triglyceride level monitoring ¹		Х	Х	Х	Х	
Dispense study medication		Х	Х	Х	Х	
Infusion given at MRMC ²		Х	Х			
Infusion given at MRMC or at the patient's home				х	х	
Adverse Events (AEs)		Х	Х	Х	х	Х
Concomitant medications		Х	Х	Х	Х	Х
Education on home PN &		v				
Omegaven		^				
Assess patient compliance				Х	Х	
Clinical supplies accounted for & destroyed						x

Table 2: Study Schedule

¹ Triglyceride level monitoring will occur daily from the time the patient begins Omegaven dosing until Omegaven dosing is complete.

² Infusions will be given at MRMC for 2-5 days, after which the infusions can be moved to the patient's home.

4.2. Study Procedures by Visit

4.2.1. Screening Visit

Cancer patients with hepatic injury will be offered Omegaven for compassionate use situations when there are no satisfactory alternative treatments. Patients meeting the criteria for this study will be screened for participation at the MRMC. The following will occur for all patients at the Screening Visit:

- Prior to performing any study procedures, the patient will be informed about the trial and asked to sign and date the Informed Consent Form (ICF). The person who conducted the informed consent discussion will also be required to sign and date the ICF.
- Patient eligibility will be assessed based on the inclusion and exclusion criteria (Sections 5.1 and 5.2).
- A complete physical examination with vital signs and medical history and historical medications will be done.
- Blood will be drawn for hematology and chemistry lab panels (see Section 4.3.1).

4.2.2. Day 1 Visit

The Day 1 Visit and the Screening Visit can occur on the same day. The Day 1 Visit will occur at CTCA, and the following will occur at this visit:

- Blood will be drawn for hematology and chemistry lab panels (see Section 4.3.1).
- Any medication changes and/or medications taken since the Screening Visit will be recorded.
- Education will be provided by site personnel on Omegaven and on home PN for those patients who will be receiving infusions in their homes.

Patients will be treated with an initial dose of Omegaven at 0.1 g/kg body weight (1ml/kg) by continuous infusion at CTCA. The infusion rate will not exceed 0.5mL Omegaven/kg body weight/hr (corresponding to 0.05g fish oil/kg/hr). Triglycerides (TGs) will be monitored daily and a dose reduction will occur if:

- TG levels rise above 400 mg/dL,
- \circ If evidence of bleeding occurs.
- Any changes to the patient's health (Adverse Events/AEs) from the time infusion begins will be recorded.

4.2.3. Day 2 Visit

The Day 2/Day 3 Visit will occur at CTCA. At this visit, the following will occur for all patients:

- Vital signs will be taken.
- Blood will be drawn for hematology and chemistry lab panels (see Section 4.3.1).
- Omegaven dosing will occur via continuous infusion at CTCA. The infusion rate will not exceed 0.5mL Omegaven/kg body weight/hr (corresponding to 0.05g fish oil/kg/hr).
- The Omegaven dose will be increased to 0.2 g/kg body weight (2 ml/kg).
- AEs and Concomitant Medications since the previous visit will be recorded.

4.2.4. Day 3 Visit

The Day 3 Visit may occur at the patient's home. At the Day 3 Visit, the following will occur for all patients:

- Vital signs will be taken.
- Blood will be drawn for hematology and chemistry lab panels (see Section 4.3.1).
- Omegaven dosing will occur via continuous infusion at either CTCA or in the patient's home. The Omegaven dose will remain at 0.2 g/kg body weight (2 ml/kg). The infusion rate will not exceed 0.5mL Omegaven/kg body weight/hr (corresponding to 0.05g fish oil/kg/hr).

- AEs and Concomitant Medications since the previous visit will be recorded.
- Drug accountability will be performed by the homecare nurse to assess patient compliance if the patient has received doses in the home without a nurse present.

4.2.5. Weekly Visits During Home Use of Omegaven (up to 4 weeks of treatment)

Patients will be monitored by healthcare nurses during home health visits every week until withdrawal from the study. The first weekly visit will occur 7 \pm 1 days after the first dose, and continue every 7 \pm 1 days thereafter. During these home health visits the following will occur:

- Vital signs will be taken.
- Blood will be drawn for hematology and chemistry lab panels (see Section 4.3.1).
- Omegaven dosing will occur via continuous infusion at either CTCA or in the patient's home. The Omegaven dose will remain at 0.2 g/kg body weight (2 ml/kg). The infusion rate will not exceed 0.5mL Omegaven/kg body weight/hr (corresponding to 0.05g fish oil/kg/hr).
- AEs and Concomitant Medications since the previous visit will be recorded.
- Drug accountability will be performed by the homecare nurse to assess patient compliance if the patient has received doses in the home without a nurse present.

Omegaven will be given for:

- 4 weeks, or
- Until serum bilirubin is < 2 mg/dL, or
- Until normalization in liver function tests.

4.2.6. Final Study Visit/Early Withdrawal Visit

At the patient's Final Study Visit/Early Withdrawal Visit, the following will occur:

- A physical exam will be performed.
- Vital signs will be taken.
- Blood will be drawn for hematology and chemistry lab panels and additional toxicity labs (see Section 4.3.1).
- AEs and Concomitant Medications since the previous visit will be recorded.
- Drug accountability will be performed by the homecare nurse to assess patient compliance if the patient has received doses in the home without a nurse present.
- Any remaining clinical supplies will be accounted for and destroyed.

4.3. Description of Study-Specific Procedures

4.3.1. Diagnostic Tests

The following diagnostic laboratory tests will be performed:

• Blood Hematology and Chemistry

 Hematology: white blood cell count (WBC or leukocyte count), WBC differential count, red blood cell count (RBC or erythrocyte count), hematocrit (Hct), hemoglobin (Hbg), mean corpuscular volume (MCV), mean corpuscular hemoglobin (MCH), mean corpuscular hemoglobin concentration (MCHC), red cell distribution width (RDW), platelet count, and mean platelet volume (MPV)

- Chemistry: Blood Urea Nitrogen (BUN), carbon dioxide (CO₂), creatinine, glucose, serum chloride, serum potassium, serum sodium, serum calcium, serum phosphorus, serum magnesium, triglycerides and a liver panel: alanine aminotransferase (ALT), aspartate aminotransferase (AST), gamma-glutamyl transferase (GGT), alkaline phosphatase (ALP), albumin, total protein, direct bilirubin (conjugated), total bilirubin
- Additional Labs: An additional clot tube of blood will be collected and stored at baseline and at the end of 4 weeks or withdrawal from study to evaluate treatment response.

The investigator, or a qualified designee who is part of the study team, will promptly review each lab report as it becomes available. If the investigator deems a value outside the reference range to be "clinically significant," then she/he will record it as an adverse event (AE). Lab reports will become a part of the source documentation.

5. SELECTION AND WITHDRAWAL OF PATIENTS

5.1. Patient Inclusion Criteria

A patient must meet the following criteria to be included in this study:

- I.1 Male of Female; ages 18 to 80
- I.2 Receiving treatment at CTCA
- I.3 Receiving PN (either in the infusion center or at home)
- I.4 Have existing hepatic dysfunction defined as Elevation of >3x the normal level of one or more of the following: Alkaline Phosphatase (ALP), Aspartate Aminotransferase (AST), or Alanine Aminotransferase (ALT) and/or Bilirubin > 2 mg/dl in the absence of biliary obstruction.
- 1.5 Able to provide informed written consent (patient or legally acceptable representative)

5.2. Patient Exclusion Criteria

A patient will be excluded from the study for any of the following reasons:

- E.1 Hypertriglyceridemia (fasting triglycerides [TG] > 400)
- E.2 Allergy to fish or egg protein
- E.3 Currently on therapeutic doses of Coumadin, heparin, or low molecular weight heparin.
- E.4 Hemodynamically unstable
- E.5 Bilirubin > 5 mg/dL
- E.6 Documented progression of liver metastases
- E.7 Unstable diabetes with known diabetic ketoacidosis within 7 days of screening
- E.8 Recent cardiac infarction taking plavix
- E.9 Severe hemorrhagic disorders
- E.10 Embolism
- E.11 Sepsis
- E.12 Undefined coma status
- E.13 Renal insufficiency defined as creatinine clearance < 30 mL/min.
- E.14 Pregnancy or lactation

5.3. Patient Withdrawal Criteria

Patients may be terminated from the study for the following events and reasons:

- W.1 The patient chooses to withdraw for any reason
- W.2 The Investigator chooses to terminate the patient from the study. Reasons could include:

- a. Occurrence of AEs related to the use of Omegaven; adverse reaction to Omegaven
- b. Patient non-compliance
- c. Patient discovered after enrollment not to have met the protocol entrance criteria
- W.3 Therapy goals are reached: patient able to meet and sustain nutrient needs by oral nutrition
- W.4 Patient lost to follow-up
- W.5 The principal-investigator terminates the study
- W.6 If bilirubin elevates to > 5 mg/dl due to obstruction
- W.7 Requires open surgical procedure
- W.8 Documented progression of liver metastases contributing to worsening of hepatic dysfunction.

If a patient does not return for a scheduled visit every effort should be made to contact the patient. In any circumstance, every effort should be made to document patient outcome, if possible. Patients will only be considered lost to follow-up if study personnel are unable to communicate with the patient or the patient's legally acceptable representative by three telephone attempts and certified letter. Reasons for withdrawal will be specified in the patient's study file, and will include date of discontinuation of investigational product and date of study withdrawal.

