9.3. Serious Adverse Event (SAE) Recording/Reporting

An SAE for this study is one that meets any one of the following criteria:

- Fatal or life-threatening
- Requires or prolongs in-patient hospitalization
- Results in persistent or significant disability/incapacity
- Important medical event

Medical and scientific judgment should be exercised in deciding whether an important medical event is serious. Although the event may not be immediately life threatening, fatal, or result in hospitalization, it should be considered serious when it jeopardizes the patient, or requires an intervention to prevent a serious outcome as defined above. Examples of serious medically important events are: intensive treatment in an emergency room or at home for allergic bronchospasm; blood dyscrasia or convulsion that do not result in hospitalization.

The term "life threatening" in the definition of "serious" refers to an event in which the patient was at risk of death at the time of the event; it does not refer to an event that hypothetically might have caused death if it were more severe. The term "in-patient hospitalization" in the definition of "serious" refers to an event in which the patient was admitted to the hospital for one or more days, even if release on the same day; or an emergency room visit, which results in admission to the hospital. Emergency room visits that do not result in admission to the hospital should be evaluated for one of the other serious outcomes criteria (e.g., important medical event).

The SAE reporting period begins at the time the first Omegaven infusion is administered and ends at the last study visit. SAEs that are considered at least possibly related to the study medication or that occur in a pregnancy that began while the patient was using the study medication can be reported at any time.

All SAEs will be followed through resolution or until the investigator attributes the SAEs to a cause other than the study medication or assesses them as chronic or stable. Follow-up SAE reports should adhere to the same procedures and timelines as initial reports. In addition, any SAE that occurs subsequent to the reporting period that the investigator assesses as possibly related to the study medication should also be considered for follow-up.

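### After withdrawal from the study, no check of death or later resolution is scheduled up to Day 28, although an efficacy variable is time to resolution or death

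*Protocol*

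**What the plan says.** - **Outcome.** The synopsis lists "Time to resolution of bilirubin or death" among the efficacy variables, next to an average improvement in bilirubin, ALP, AST and ALT for which no time point is given.
- **Withdrawal.** Section 5.3 opens with "Patients may be terminated from the study for the following events and reasons". Two of its criteria involve a worsening liver: W.6, "If bilirubin elevates to > 5 mg/dl due to obstruction", and W.8, "Documented progression of liver metastases contributing to worsening of hepatic dysfunction". One is a favourable exit: W.3, "Therapy goals are reached: patient able to meet and sustain nutrient needs by oral nutrition".
- **Scheduled follow-up.** Section 4.2.5 provides "home health visits every week until withdrawal from the study". Table 2 has no column after the Final Study/Early Withdrawal visit.
- **Safety window.** Under 9.3 the SAE period "ends at the last study visit"; the AE period in 9.2 closes at the same point.
- **Outcome after exit.** Section 5.3 adds "In any circumstance, every effort should be made to document patient outcome, if possible".
- **Analysis.** Section 10.4 is descriptive. It includes every dosed patient, summarises laboratory change to the worst follow-up value, reports resolution as an incidence, and makes time to resolution optional.

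**The concern.** A variable that includes death needs death to be looked for over the same period in everyone. Here the scheduled search stops when a patient leaves the study, and leaving can be prompted by a deteriorating liver in patients with advanced cancer. Exits under W.6 and W.8 are therefore likely to be informative: patients who leave for these reasons probably differ, in their chance of dying or resolving by Day 28, from those who stay.

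The trial has one arm and about 30 patients. No comparator would share the same loss, so a few unrecorded outcomes can visibly move the result. How withdrawals are handled in the analysis can be left to an SAP, but an SAP cannot supply data that the protocol never arranged to collect.

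**Working it through.** **1. What is collected after exit**

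| Source | What it gives after a W.6 or W.8 exit | What it leaves open |
|---|---|---|
| 4.2.6, Early Withdrawal visit | One full liver panel and AEs at exit | Later course; survival |
| 4.2.5, weekly visits | Nothing; they stop at withdrawal | Laboratory values to Day 28 |
| 9.3, open SAEs | Follow-up to resolution, chronic or stable status, or attribution to a cause other than the drug | W.6 and W.8 name such a cause (obstruction, metastases), so follow-up may stop early |
| 9.3, late SAEs | Reportable at any time if at least possibly drug-related | A death put down to metastatic progression would probably not qualify |
| 5.3, outcome sentence | An effort to document outcome | No date, method or definition of outcome |

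None of these schedules a vital-status check at a common date.

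**2. Which results are exposed**

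- *Resolution incidence (10.4):* all dosed patients stay in the denominator. A patient who leaves unresolved counts as unresolved, and only a later resolution is missed. Largely protected.
- *Worst-value laboratory change (10.4):* the exit panel enters. Largely protected.
- *Average improvement (synopsis):* the exit value is available, the later course is not. Partly exposed.
- *Time to resolution or death (synopsis):* deaths and resolutions after exit are not systematically recorded. Exposed.

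**3. Size**

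The protocol has no figure to reproduce. Section 10.2 gives 30 patients and no withdrawal, death or resolution rate. One unrecorded outcome is 1/30 = 3.3 percentage points (1/50 = 2.0 if enrolment reaches the synopsis maximum of 50). Every rate below is an assumption, used only to show direction and rough scale.

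*(a) Mean bilirubin change, n = 30.* Assume stayers change by −0.5 mg/dL and withdrawn patients by +1.5 at the exit visit and +3.0 at week 4.

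| Withdrawn | Left out | Exit value used | Followed to week 4 |
|---|---|---|---|
| 3 | −0.50 | (27×−0.5 + 3×1.5)/30 = −0.30 | (27×−0.5 + 3×3.0)/30 = −0.15 |
| 6 | −0.50 | (24×−0.5 + 6×1.5)/30 = −0.10 | (24×−0.5 + 6×3.0)/30 = +0.20 |

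The exit panel recovers 0.20 of 0.35, or 0.40 of 0.70, which is 57% of the gap in both cases.

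*(b) Day-28 resolution or death.* Assume 50% of stayers resolve by Day 28 at a constant hazard. Withdrawn patients leave uniformly on Days 7–21, do not resolve, and then have a mean survival of 10 days. Their probability of death by Day 28 is 1 − (10/14)(e^−0.7 − e^−2.1) = 0.733.

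| Withdrawn | True resolution | True composite | Censored at exit |
|---|---|---|---|
| 10% | 0.9×0.5 = 45.0% | 45.0 + 0.1×73.3 = 52.3% | 47.8% |
| 20% | 0.8×0.5 = 40.0% | 40.0 + 0.2×73.3 = 54.7% | 45.6% |

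The last column is 1 − exp(−∫h dt) over Days 0–28, by numerical integration. Here h is the rate of new resolutions divided by the proportion still under observation. All deaths in this scenario follow exit, so one censored figure serves both outcomes. It is 4.5 to 9.1 points below the true composite and 2.8 to 5.6 points above true resolution.

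*(c) Resolution alone, n = 30.* Assume 8 resolved and 5, 9 or 12 withdrawn unresolved, all at uniform times on Days 3–28. The mean Kaplan–Meier estimate at Day 28 (20,000 simulated samples each) is 29.5%, 32.5% or 35.5%. The incidence over all dosed patients is 8/30 = 26.7%.

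**The case against.** The strongest reply is that the protocol protects these patients better than the withdrawal list suggests. They have an exit visit with a liver panel, remain in the analysed population, and contribute their worst values. The protocol records the date of stopping drug and the date of leaving the study separately. Loss to follow-up requires three calls and a certified letter. Time to resolution is optional in 10.4, and no censoring rule is written; one may sit in an SAP that is not shown. All of this stands. It confines the problem to the period after exit and to two outcomes.

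A reader might still infer something stronger, which the text does not support:

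- *That all follow-up and all capture of death end at withdrawal.* Open SAEs continue to be followed, possibly related SAEs can be reported later, and outcome is to be documented if possible. What ends is scheduled ascertainment.
- *That exactly the patients who do badly are lost.* The list is permissive. W.6 requires obstruction and W.8 requires metastatic progression; worsening PN-induced injury alone is not a criterion. W.3 is a good outcome that also ends participation.
- *That the result favours the drug.* The composite joins a good event and a bad one, so missed deaths lower it. Only resolution taken alone is overstated, and only if withdrawals are censored.
- *That W.6 and W.8 exits must count as failure on the primary objective.* That objective concerns PN-induced dysfunction. Whether obstruction or tumour progression belongs in it is a choice of estimand, not an error in the protocol.

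**Conclusion.** The point holds as a gap in data collection. For a patient who leaves early, neither death nor later resolution is systematically ascertained between exit and Day 28, and the existing safeguards do not close that gap for W.6 and W.8 exits. The time-to-event variable is affected most and the average improvement in part; the incidence and worst-value summaries in 10.4 are largely sound. No overall direction of bias can be claimed. The size cannot be derived from the protocol: about 3 percentage points per unrecorded outcome at 30 patients is firm arithmetic, while the 3 to 9 point shifts in illustration (b) depend wholly on the assumed rates and on censoring at exit. This is a modest, cheap improvement to the protocol and does not invalidate the study.

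**What to change.** - **Section 5.3:** for every dosed patient who stops Omegaven or leaves early, record vital status at Day 28 by chart or telephone, and collect any bilirubin or liver panel already drawn up to Day 28. Exempt patients who withdraw consent to follow-up.
- **Section 10.4:** keep all dosed patients in the denominator, report death separately from resolution, and show W.3, W.6 and W.8 exits as separate categories.

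The cost is one chart check or call per withdrawn patient and a short addition to each of the two sections. No extra blood draw is needed, and nothing changes about when treatment stops.
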